#### *Aim 2 Health and Recovery Outcomes: Collected at baseline, posttreatment, 6 & 9 months*

Used in the CBTw pilot studies and across the SMI literature, subjective recovery pertinent to work will be measured using the Recovery Assessment Scale (RAS), a 41 item, self-report measure with higher scores indicating stronger recovery attitudes (scored on a 1 to 4 Likert scale); the RAS was developed and validated in people with SMI.

Psychiatric symptoms will be assessed using the adult version DSM-5 Level 1 Cross-Cutting Symptom Measure (CCSM), a 23-item, Likert response (scored on a 0 to 4 scale), self-rated instrument that assesses 13 domains that are important across SMI diagnoses (e.g., depression, anxiety, psychosis, mania, sleep problems, self-harm, substance use, etc.) with higher scores indicating more severe total symptoms. The CCSM has been found to have strong validity and reliability in SMI samples.

Health-related quality of life will be examined using the SF-12 comprised of the Physical Component Summary (PCS) and Mental Component Summary (MCS). The PCS and MCS are standardized with a mean of 50 and a standard deviation of 10, with higher scores indicating better health-related quality of life. The subscales have good reliability and are predictive of health outcomes in Veterans with chronic illness.

Suicidality will be assessed with the 21-item Scale for Suicidal Ideation (SSI), an interviewer rated measure of a continuum of suicidal ideation, including thoughts, attitudes, plans, and behaviors. SSI items are scored on a 0 to 2 Likert scale, with higher scores indicating greater intensity of suicidal ideation. The SSI has strong psychometric properties in outpatients with psychiatric conditions.

Collected from a CAPRI/CPRS/JLV data pull, service utilization data will include days of psychiatric hospitalizations. Lead by [name], this service utilization data will be extracted from the Corporate Data Warehouse.

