Aim 2: Health and recovery outcomes. Two-level linear regression models accounting for the nested nature of the data (repeated measures nested within individuals) will be used to examine the effects of CBTw + SE services compared to psychoeducation + SE on the change of each of the continuous outcomes including recovery (RAS), health-related quality of life (PCS & MCS), symptoms (DSM), and suicidality (SSI) over time (baseline and 3-, 6-, 9-months follow-ups). It is expected that there will be adequate power (>80%) to detect the treatment effect on health and recovery outcomes even if the effect size is small (i.e., $f^2 = .03$). *Regarding the outcome of suicidal ideation, it is anticipated that the range of responses will be smaller, given that fewer participants will report these thoughts (21.2% of participants in the CBTw open pilot reported passive ideation at baseline; 9.6% reported such thoughts at follow up). Thus, the study may be less powered to detect a treatment effect. However, despite this issue of range restriction given the relatively lower base rate of suicidal thoughts, WORKWELL will nonetheless examine possible treatment effects, due to the importance of this outcome in Veterans with SMI.*

Preliminary analysis: Baseline characteristics of sample & covariates analyses

Given the RCT design, characteristics of participants are expected to be balanced across the two study arms. Baseline characteristics and baseline clinical outcomes (e.g., symptoms) will be compared between the arms using the appropriate test (i.e., t-test, or Chi-square test). Variables found to significantly differ will be included as covariates in the primary analyses. All primary analyses will also include time receiving SE services and site membership as covariates. The potential interaction effects of site with key predictors will also be included as predictors to account for the site effect. Lastly, attendance (the number of CBTw or psychoeducation sessions attended) and the association with the Aim 1 and Aim 2 outcomes will be examined.

Aim 1 Analyses: Competitive Work Outcomes

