Hypothesis 1: For the outcome, total weeks worked in competitive jobs, three-level linear regression models will be used to test the effects of CBTw + SE compared to psychoeducation + SE over time, with predictors of study arm, arm by time interaction, site, and interaction between site and key predictors, covariates, as well as random effects to accommodate the potential non-independence due to repeated measures and group cohort effects. The time effects could be linear or nonlinear; these possibilities will be examined by treating time as continuous or categorical. If the outcomes are not normally distributed, robust maximum likelihood estimation method will be used to correct the standard error estimates for nonnormality. In the case of excess of zeros for this outcome, hurdle negative binomial models, a reliable method to analyze zero inflated longitudinal data of this nature, will be utilized. For the binary outcome, steady competitive work status across the 9-month study period, two-level logistic regression model will be used with the same set of predictors as in the linear models, with random effects to accommodate the potential non-independence due to group cohort effects.

Aim 2 Analyses: Health and Recovery Outcomes

To test **Hypothesis 2a**, Two-level linear regression models accounting for the nested nature of the data (repeated measures nested within individuals) will be used to examine the effects of CBTw + SE services compared to psychoeducation + SE on the change of each of the continuous outcomes including recovery (RAS), health-related quality of life (PCS & MCS), symptoms (DSM), and suicidality (SSI) over time (baseline and 3-, 6-, 9-months follow-ups). The scores of the outcome measures are calculated by averaging the corresponding items. The models are the same as those in Aim 1 analysis except that the outcomes are different. It is hypothesized that CBTw + SE will lead to a greater improvement on the health and recovery outcomes (indicated by a significant arm by time effect). If the outcomes are not normally distributed, robust maximum likelihood estimation method will be used to correct the standard error estimates for nonnormality.

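### The SAP's item-averaging rule makes no exception for the SF-12 PCS and MCS, which the protocol defines as scores standardized to mean 50, SD 10

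*SAP*

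**What the plan says.** **SAP, Aim 2 Analyses: Health and Recovery Outcomes, Hypothesis 2a.** The continuous outcomes are recovery (RAS) and then "health-related quality of life (PCS & MCS), symptoms (DSM), and suicidality (SSI) over time". The next sentence is the scoring rule: "The scores of the outcome measures are calculated by averaging the corresponding items". The SAP has no other scoring instruction for these measures.

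**Protocol, Study Evaluations, Aim 2 Health and Recovery Outcomes.** The SF-12 is described differently from the other questionnaires. For quality of life, "Health-related quality of life will be examined using the SF-12 comprised of the Physical Component Summary (PCS) and Mental Component Summary (MCS"), with a scale-construction source cited as reference 84. Then: "The PCS and MCS are standardized with a mean of 50 and a standard deviation of 10". No item codes, weights, item allocation or algorithm are given.

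The other three instruments are described by their item codes. RAS is "scored on a 1 to 4 Likert scale". The CCSM, which the SAP calls DSM, has items coded 0 to 4, "with higher scores indicating more severe total symptoms". For suicidality, "SSI items are scored on a 0 to 2 Likert scale".

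The protocol's own Data Analysis section has no averaging rule. The rule appears only in the SAP.

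**The concern.** One rule is applied to two kinds of score. RAS, CCSM and SSI are sets of items sharing a response scale, and an item mean suits them. The protocol defines PCS and MCS as summaries on a standardized metric. An analyst working from the SAP would average SF-12 items; one working from the protocol would produce standardized scores. The two would report different variables under the same names.

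What is at stake is the meaning of the quality-of-life result. A difference in item-mean units cannot be read as points on a scale with SD 10, nor set beside other results reported on that scale. The scores also enter Hypothesis 2b, both as outcomes and as baseline adjustment. Leaving two scorings open until the data are seen would also allow a choice between them after the fact.

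**Working it through.** The plan gives no numerical result for this scoring, so there is none to reproduce. The check sets the passages side by side, then asks what a change of scoring can and cannot do.

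**1. Does the rule fit each listed outcome?**

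| Outcome in the SAP list | Protocol description | Item mean compatible? |
|---|---|---|
| RAS | items coded 1 to 4 | yes |
| DSM (CCSM) | items coded 0 to 4, total severity | yes; with complete items, mean = total / 23 |
| SSI | items coded 0 to 2 | yes; with complete items, mean = total / 21 |
| PCS | standardized, mean 50, SD 10 | no |
| MCS | standardized, mean 50, SD 10 | no |

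Two of five do not fit.

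**2. Can an item average be on the 50/10 metric?** For items x₁…x_k, the mean is at most the largest item code. The documents do not give the SF-12 codes. Assume a top code anywhere from 3 to 6: the average is then at most 3 to 6. The standard deviation of a variable confined to an interval is at most half its width, so with codes from 0 to 6 it is at most (6 − 0)/2 = 3. Neither a mean of 50 nor an SD of 10 is reachable without a further norming step, and the SAP states none.

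**3. Does a change of metric alone alter the test?** If the two scorings are linked by T = a + bX with b > 0, the arm difference and its standard error are both multiplied by b, so their ratio is unchanged. One simulated data set (120 per arm, 12 items, all inputs assumed) shows this:

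| Score | Arm difference | t | p |
|---|---|---|---|
| Item mean | 0.25 | 2.809 | 0.0054 |
| Item sum (mean × 12) | 3.04 | 2.809 | 0.0054 |
| 50/10-type rescaling, 50 + 10(mean − 3)/0.9 | 2.82 | 2.809 | 0.0054 |

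The same reasoning covers the arm-by-time coefficient in a linear model. The SAP's Aim 2 power statement, "adequate power (>80%) to detect the treatment effect on health and recovery outcomes even if the effect size is small", is given as f² = .03 and not in PCS or MCS points, so a change of metric does not touch it either.

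**4. When would the test change?** Only if averaging also changes the item weights or the items in each score. Neither document says which items are the corresponding ones. To show that this could matter, assume two domains of six items each, every item equal to 0.8 × its domain's latent score plus unit-variance noise, a 0.36 SD arm effect on one domain's latent score only, inter-domain correlation ρ, 120 per arm, and two-sided alpha .05.

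- Average of the affected domain's own items: d = 0.8 × 0.36 / √(0.64 + 1/6) = 0.321. Noncentrality is 0.321 × √60 = 2.48, and power is about 70%.
- Average of all 12 items: d = 0.144 / √[0.25 × (1.28 + 1.28ρ + 1/3)].

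| ρ | d, all 12 items | Power (noncentral t) | Power (2,000 simulations) |
|---|---|---|---|
| 0 | 0.227 | 42% | 41% |
| 0.3 | 0.204 | 35% | 34% |
| 0.6 | 0.187 | 30% | 28% |

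This illustrates a mechanism under assumed inputs. It does not estimate what would happen in WORKWELL.

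**The case against.** The strongest reply is that the averaging sentence is a generic line written with the Likert scales in mind. The same paragraph still calls the outcomes PCS and MCS, which the protocol has already defined, and nothing in the SAP says that definition is replaced. The intent may well be to use the standardized scores. That is fair, and it rules out saying that a non-standard score will be reported. It does not remove the conflict, because the sentence carries no exception and is the SAP's only scoring instruction.

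A reader might infer that the quality-of-life results would be wrong. The documents do not support that. A pure metric change leaves t and p as they were, and the SAP's stated criterion for Hypothesis 2a is a significant arm-by-time effect. Harm to the inference is conditional on weights or item allocation that neither document gives.

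A reader might also infer that every Aim 2 measure is affected. It is not. Inpatient days come from records and have no items, and the rule suits RAS, CCSM and SSI.

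Finally, these are secondary outcomes, and the items can be rescored at any time. Both points stand and limit the severity.

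**Conclusion.** The conflict is real and is one of stated rules, not of missing detail: the SAP's averaging sentence covers PCS and MCS, and an unnormed item average cannot be the score the protocol defines. It affects two of the five continuous Aim 2 outcomes and the whole quality-of-life component of Hypothesis 2a. The established consequence is that the scores would not be those the protocol names and could not be interpreted on the 50/10 metric.

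No bias or loss of power is established. The arm-by-time test changes only if averaging also changes item weights or allocation.

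Total weeks worked, the primary outcome, is not scored by this rule. One indirect route exists: the SAP adds baseline clinical variables that differ between arms as covariates in the primary analyses. That selection, too, is unchanged by a linear rescaling and could shift only if the composite itself changed.

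The range argument assumes SF-12 item codes no higher than 6; the conclusion would need codes near 50 to fail. Nothing here relies on knowledge of SF-12 item weights. Severity is moderate: a secondary-outcome correction to make before scoring.

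**What to change.** Replace the averaging sentence in the SAP with text to this effect:

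> RAS, CCSM and SSI scores are item means. PCS and MCS are the standardized SF-12 summaries (mean 50, SD 10) defined in the protocol's Aim 2 measures, computed by the scoring method of the source cited there.

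Keep item means for the first three scales and do not offer totals as an alternative. Participants may decline any question, and with skipped items the mean of the answered items is no longer proportional to the total, so an open choice would loosen a rule that is now definite. For the same reason it would help to state how skipped items are handled on each scale.

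The cost is one SAP sentence and some scoring code. The SF-12 is already part of the planned assessments, so data collection, sample size and the primary analysis model do not change. The revision should be dated before any Aim 2 score is computed.

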#### *Health and Recovery Outcomes (Hypotheses 2a & 2b)*

To test **Hypothesis 2a**, three-level linear regression models (i.e. mixed models) accounting for the nested nature of the data will be used to test the effects of CBTw + SE services compared to psychoeducation + SE on each of the continuous outcomes including recovery (RAS), health-related quality of life (PCS & MCS), symptoms (CCSM), and suicidality (SSI) over time. For the count outcome of service utilization, three level Poisson regressions will be used to examine group differences over time on number of days of inpatient hospitalization. If there is a problem of excess of zeros for utilization (e.g., no hospitalizations), hurdle negative binomial models will be used.

To test **Hypothesis 2b**, three-level linear regression models will examine the effects of work on health and recovery outcomes over time, with predictors of competitive weeks worked, time, weeks by time interaction, site membership and potential interaction between site and key predictors, potential covariates (i.e. controlling for baseline levels of health and recovery), as well as random effects to accommodate the potential non-independence due to repeated measures and group cohort effects.

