To test **Hypothesis 2b**, two-level linear regression models will examine the effects of work on health and recovery outcomes over time, with predictors of competitive weeks worked, time, weeks by time interaction, site membership and potential interaction between site and key predictors, potential covariates (i.e. controlling for baseline levels of health and recovery), as well as random effects to accommodate the potential non-independence due to repeated measures and group cohort effects.

Missing data: Aims 1 & 2

Missing data from Aims 1 and 2 will come in two different forms: missing by attrition and intermittent missing of observation. Using logistic regression, the effects of missing observations due to sample attrition will be examined by investigating the participant characteristics associated with dropout. If results reveal that data are missing completely at random (MCAR) or due to observed factors (MAR), the data will be analyzed using full information maximum likelihood, taking into account potential predictors for missingness. However, if the pattern of missing data is nonignorable, pattern-mixture models that includes variables defined by the participant's pattern of missing data will be used. Sensitivity analyses also will be performed to examine how the result will change based on different assumptions about the missing data, such as the missing work period having no work, the mean amount of work as available data from earlier follow-up periods, or full employment.

Account for Heterogeneity in the Sample

The study is limited to working aged Veterans with SMI who are unemployed at baseline, decreasing the heterogeneity of the sample. In addition, analyses will examine whether treatment effect will change as a function of the site membership and major characteristics of the study participants, such as different types of SMI diagnoses, age, and current substance use (e.g., users vs. non-users).

AIM 3 CBTw IMPLEMENTATION: OVERVIEW

The initial CBTw implementation strategy was informed by implementation science and developed based on our experience in the two CBTw pilots, stakeholder surveys and interviews, and feedback from operational partners. *In order to ensure successful implementation of CBTw during WORKWELL and wide-scale uptake following its completion, an evaluation of this initial implementation strategy and barriers and facilitators of implementation will be conducted, guided by the RE-AIM framework.*

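### Free improvement: Hypothesis 2a compares change from baseline without baseline adjustment; a common baseline mean or a prespecified baseline covariate would make the same test more precise.

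*SAP*

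**What the plan says.** In the SAP, Aim 2 Analyses (Hypothesis 2a), recovery (RAS), the two SF-12 summaries (PCS and MCS), symptoms and suicidality (SSI) are modelled "over time (baseline and 3-, 6-, 9-months follow-ups", so the baseline score is an outcome value. The model is borrowed: "The models are the same as those in Aim 1 analysis except that the outcomes are different". The Hypothesis 1 paragraph gives that model as one "with predictors of study arm, arm by time interaction, site, and interaction between site and key predictors, covariates". The hypothesis is judged on the interaction: "indicated by a significant arm by time effect".

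The Preliminary analysis section of the SAP compares baseline characteristics and baseline clinical scores between arms and adds: "Variables found to significantly differ will be included as covariates in the primary analyses". The covariates that always enter are time receiving SE services and site. Site interactions with key predictors are also included.

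For Hypothesis 2b the SAP names adjustment for the starting score ("controlling for baseline levels of health and recovery"). For 2a, the randomised comparison, it names none and does not set the arms equal at baseline. Protocol sections 5.3.2 and 5.4 place the baseline assessment before randomisation. Protocol section 5.2.1 classes health and recovery as secondary outcomes.

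**The concern.** Before randomisation the true arm difference is zero, yet the model estimates one. When the arm term is free at baseline, the interaction at a later visit subtracts the whole observed baseline difference. Only a fraction rho of that difference is expected to persist, so the subtraction adds noise. In a trial where the arms happen to differ at the start, it also tilts the result towards the arm that began worse. The scores that would avoid this are already collected. The SAP's only provision for baseline imbalance in 2a is triggered by a significance test and enters as a main effect, which is the wrong place to influence an interaction.

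At stake is precision on five continuous secondary outcomes. One of them is suicidality, for which the SAP already expects reduced power.

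**Working it through.** **The plan's own figure.** The SAP gives Aim 2 power only as above 80% at f² = .03, with no visit structure or correlation for these scales, so it cannot be reproduced. At f² = .03 and two-sided .05 (sidedness assumed), a noncentral F calculation gives:
- 276 independent participants: 81.8%
- 240 independent participants (276 × 0.87): 76.2%
- 240 with three visits and the repeated-measures ICC of .2: 97.5%
- the same, with the cohort ICC of .077 and cohorts of 8: 88.4%

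The SAP reports 97.6% for the Aim 1 interaction at the same f². Starting powers of 80%, 90% and 97.6% are therefore all shown below.

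**Inputs.** 138 per arm at baseline (Protocol 5.3.1); 13% attrition, so 138 × 0.87 ≈ 120 per arm at follow-up; alpha .05. Assumed: unit variance, compound symmetry, rho from 0.2 to 0.8. The SAP's ICC of .2 was estimated for weeks worked, not for these scales.

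**Variance of a single-visit contrast, n per arm, two-level model.**
- Arm term free at baseline: 4(1−rho)/n
- Common baseline mean: 2(1−rho²)/n
- Ratio, adjusted to planned: (1+rho)/2

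At rho 0.5 and n = 120 the standard errors are √(4 × 0.5/120) = 0.129 and √(2 × 0.75/120) = 0.112.

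**Power after adjustment** = Φ(δ/√ratio − 1.96), with δ = 2.80, 3.24 or 3.94 for planned power of 80%, 90% or 97.6%.

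| rho | ratio | from 80% | from 90% | from 97.6% |
|---|---|---|---|---|
| 0.2 | 0.60 | 95.1 (+15.1) | 98.7 (+8.7) | 99.9 (+2.3) |
| 0.5 | 0.75 | 89.9 (+9.9) | 96.3 (+6.3) | 99.5 (+1.9) |
| 0.7 | 0.85 | 86.0 (+6.0) | 94.0 (+4.0) | 99.0 (+1.4) |
| 0.8 | 0.90 | 84.0 (+4.0) | 92.7 (+2.7) | 98.6 (+1.0) |

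With a cohort effect acting only after baseline (ICC .077, cohorts of 8), the ratios are 0.70, 0.84, 0.92 and 0.96, and 80% becomes 92%, 86%, 83% and 82%. Without a cohort effect, a linear slope gains 17 to 4 points from 80% over the same range of rho, and the mean of the three follow-ups 19 to 6.

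**Conditional bias.** The baseline difference that just reaches significance is 1.96 × √(2/138) = 0.236 SD. The contrast is then off by (1−rho) × 0.236, which is 0.19, 0.12 and 0.07 SD at rho 0.2, 0.5 and 0.7. The conditional standard error is √(2(1−rho²)/120), and the test uses √(4(1−rho)/120). The conditional false-positive rate is 15%, 11% and 9% respectively. Averaged over the distribution of baseline differences, it is 5.0% at each rho.

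**What the covariate rule does.** In simulated complete data (rho 0.5, with 0.3 SD added to one arm's baseline to mimic an imbalance), the 9-month arm-by-time estimate was −0.423 without the baseline score as a covariate, −0.423 with it, and −0.423 as the raw difference in change. Analysis of covariance gave −0.277, and the standard error fell from 0.130 to 0.110. In a second simulated data set, with dropout (n = 276, rho 0.5), adding the score moved the last-visit estimate from −0.178 to −0.156 and its standard error from 0.1323 to 0.1309.

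**The case against.** The planned model is a standard repeated-measures analysis, and the SAP says openly that it targets change. Several stronger readings are tempting, and the documents do not support them.

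- *The test is invalid, or chance imbalance is left uncorrected.* Neither is so. The contrast subtracts the baseline difference in full, which over-corrects it. The overall error rate is nominal. The 9% to 15% rates apply only given a difference at the significance threshold; differences that large or larger occur about 5% of the time per outcome. With no imbalance, the same test rejects only about 1% to 3% of the time over rho 0.2 to 0.7.
- *The plan loses about ten points of power.* That needs rho of 0.5 and a starting power of exactly 80%. The documents give no rho, and their power figure is a lower bound.
- *The test is exactly a change-score comparison, and the covariate rule does nothing.* Both hold only for categorical time and complete data. The SAP also allows continuous time, expects 13% attrition and plans full-information maximum likelihood.
- *The Protocol shows the same model.* Its Hypothesis 2a text does not list baseline among the outcome times. It needs matching wording, but it does not by itself show the problem.

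What stands against this point is that the gain is of unknown size and falls on secondary outcomes. What stands for it is that adjustment improves precision at every rho below 1, and that the significance-test rule is no working substitute.

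**Conclusion.** The point holds as a free improvement, not as an error that undermines the analysis. As written, Hypothesis 2a gives up precision that the collected data would supply. The gain is roughly 1 to 15 points of power for a single-visit contrast, depending on rho and on the true planned power, and it is smaller if cohort effects are present. The secondary issue is conditional: in a trial with a noticeable chance imbalance, the estimate is shifted by (1−rho) times that imbalance in favour of the arm that started worse, and the stated covariate rule hardly alters this.

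These sizes rest on compound symmetry, normal approximations, 120 per arm at follow-up and an assumed rho. The direction of the precision result does not depend on the value chosen for rho.

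**What to change.** In the SAP's Hypothesis 2a paragraph, and correspondingly in the Health and Recovery Outcomes part of Protocol section 5.6, choose one of these:

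1. Keep baseline as an outcome but give both arms one common baseline mean. Drop the arm main effect and any arm-by-site term acting at baseline, so that arm and arm-by-site effects enter only at 12 weeks, 6 months and 9 months. Removing the arm term alone is not enough, because a remaining arm-by-site term would let the arms differ at baseline again.
2. Model the three follow-ups only, with the baseline score and its interaction with visit as prespecified covariates. This is similar to option 1 but not identical when data are missing; option 1 also keeps Veterans who have only a baseline or only a follow-up score.

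State that the choice applies whatever the baseline comparison shows for the outcome being modelled, and that the significance-test rule does not govern that score.

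The cost is a few sentences of text. No new data, visits or participants are needed.
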